I (investigator) also confirm that I will make the findings of the study publicly available through publication or other dissemination tools without any unnecessary delay and that an honest, accurate and transparent account of the study will be given. Any deviations from the study as planned in this protocol will be explained and reported accordingly.

Chief Investigator:

[name]

Signature:

Date 22/05/2023

Print Name (in full): [name]

Position: Associate Professor

On behalf of the Study Sponsor:

Signature:

Date 26/05/2023

Print Name (in full): [name]

Position: Research Governance Manager

STUDY SUMMARY

IDENTIFIERS		
IRAS Number	322887	
REC Reference No.		
Sponsor Reference No.	157143	
Other research reference number(s) (if applicable)	UCL data protection number: Z6364106/2023/03/03 health research	
Full (Scientific) title	Non-randomised feasibility study of point of care natural language processing using the MiADE system to assist structured clinical documentation	
Health condition(s) or problem(s) studied	Recording of diagnoses, medications and allergies in electronic health records	
Study Type i.e. Cohort etc	Non-randomised intervention study utilising mixed methods	
Aim(s):	To clinically evaluate a system to support automatic conversion of clinicians' text into structured data at the point of care.	
Objectives:	Primary: To ascertain whether the MiADE point of care NLP system increases the number of diagnoses, medication and allergies recorded by clinicians in a structured way in the electronic health record.	
	Secondary:	
	 To evaluate the usability of the MiADE system To evaluate the accuracy and technical performance of the MiADE system To evaluate the effect of using MiADE on patient consultations To explore how the MiADE system can be improved 	
Type of trial:	Single centre non-randomised intervention study	
Trial design and methods:	The trial consists of two non-randomised intervention substudies with before and after comparison (outpatient and inpatient), with embedded qualitative substudies involving clinician interviews and (in the outpatient setting only) observed consultations and patient interviews. Clinicians will be recruited, consented and provided with training to use the MiADE system. The system will be switched on at a particular time point, and clinical records for patients seen before and after the system was switched on will be compared. The primary outcome will be the comparison of the number of diagnoses, medication and allergies entered in a structured way per	

	patient. A rapid ethnography-based approach will be used to observe a subset of patient consultations to find out how clinicians are using the system, and semi-structured interviews will be held with patients and clinicians to understand the effect of social, cultural and behavioural information on human experiences and practices.
Trial duration per participant:	5 months
Key Study milestones	Jul 2023: Clinician recruitment and consent
	Aug 2023: Training of clinicians, surveys and observed consultations without MiADE
	Sep 2023: MiADE switch on
	Oct 2023: Interviews, surveys and observed consultations with MiADE
	Nov 2023: Study end
	Dec 2023 – Jan 2024: Data analysis
Estimated total trial duration:	7 months
Planned trial sites:	Single-site, UCLH
Total number of	Outpatient study:
participants planned:	Clinicians using MiADE: at least 25, target 50
	Patients for analysis of pseudonymised health record: estimated 3000 (assuming 25 clinicians each see 5 new patients per week, and 24 weeks of data are analysed)
	Clinicians for observed consultations and interview: 5
	Patients for observed consultation and interview: at least 20 (10 before MiADE, 10 after MiADE)
	Inpatient study:
	Clinicians using MiADE: at least 25, target 50
	Patients for analysis of pseudonymised health record: estimated 600 (assuming 5 inpatient teams each discharge 5 patients per week, and 24 weeks of data are analysed)
Main inclusion/exclusion criteria:	Electronic health record of patients being seen in clinics under the care of participating clinicians
Statistical methodology	Outpatients: comparison (pre- and post-intervention) of mean

Feasibility study of 'MiADE' point of care natural language processing, EDGE number 157134, IRAS number 322887, Protocol, Version 1.1, DATE 24/07/2023

and analysis:	number per patient of problems, medications and allergies recorded in structured data by the clinician.
	Outpatient observation substudy: comparison (pre- and post- intervention) of proportion of problems, medications and allergies recorded in structured data per patient, with manual review of free text clinical notes considered the 'gold standard'. Descriptive summary statistics will be used to describe the participant demographics for observations and interviews, and qualitative results will be analysed using thematic analysis mapped to the theoretical domains framework.
	Inpatients: comparison (pre- and post-intervention) of proportion of ICD-10 coded diagnoses for hospital admission which have a corresponding structured problem list entry.
FUNDING & OTHER	
Funding	National Institute of Health Research
Other support	Support from the UCL/UCLH NIHR Biomedical Research Centre and the Clinical and Research Informatics Unit
STORAGE of SAMPLES / DA	ΓA (if applicable)
Human tissue samples	Not applicable
Data collected / Storage	The MiADE system will be implemented wholly within the hospital (UCLH) network. All research data will be stored on UCLH servers or in the UCL Data Safe Haven.
KEY STUDY CONTACTS	
Committees	The overall NIHR funded project of which this study is a part is overseen by the MiADE steering committee. The project co-leads ([name] and [name]) jointly chair the MiADE steering committee.
Sub-contractors	None
Other relevant study personnel	Project co-lead and Chief Research Information Officer, UCLH: [name] Lead for clinician engagement: [name] Software developers: [name], [name] Natural language processing expert: [name] Clinical data standards lead: [name] Clinical safety and evaluation of digital health interventions: [name] Human-computer interaction expert: [name]

KEY ROLES AND RESPONSIBILITIES

SPONSOR: The sponsor is responsible for ensuring before a study begins that arrangements are in place for the research team to access resources and support to deliver the research as proposed and allocate responsibilities for the management, monitoring and reporting of the research. The Sponsor also must be satisfied there is agreement on appropriate arrangements to record, report and review significant developments as the research proceeds, and approve any modifications to the design.

1. INTRODUCTION

MiADE is a natural language processing system designed to be embedded within electronic health records to enable unstructured text entered by clinicians to be converted into structured data in real time. Structured entries (such as diagnoses, medication and allergies) extracted from the text are presented to the clinician for validation, and can be amended or corrected before being committed to the record. The system is designed to make it easier for clinicians to enter structured data and hence improve the completeness and quality of data in electronic health records (Figure 1).

This study aims to evaluate MiADE to assess its performance and utility, and gather information to inform future improvements and developments. The evaluation consists of two before-and-after studies with qualitative and quantitative assessment. Study 1 will be conducted in the outpatient setting, in which the number of structured entries per patient will be compared before and after switching on the MiADE system, and feedback will be gathered from clinicians. A detailed qualitative substudy will recruit clinicians and patients for observed consultations and semi-structured interviews. Study 2 will take place within the inpatient setting, where inpatient clinical teams will be recruited and surveyed, and electronic health records of patients will be compared before and after MiADE system was switched on.

The findings from this study will be used to support further improvement and roll out of natural language processing at the point of care.

2. BACKGROUND AND RATIONALE

The need for structured data in electronic health records

This NIHR funded project aims to develop a natural language processing (NLP) system to make it easier for clinicians to record structured data in electronic health records (EHRs) for patient care and research. High quality data are essential to realise the benefits of the NHS Long Term Plan [1] such as early diagnosis, better coordination of care and avoidance of unnecessary admissions. The everincreasing knowledge base in medicine and complexity of treatments makes computer-assisted decision support increasingly important. Detailed recording of patients' clinical characteristics (phenotype) is essential for precision medicine initiatives [2]. In the Chief Medical Officer's 2016 annual report, Dame Sally Davies stated that "in order to deliver [genomic medicine services] we will also need national standards for defining the symptoms (the phenotype) of patients in a systematic way." [3]

It has long been recognised that well-organised medical records are essential for high quality patient care [4], but today's records are far from ideal. Although patient data are increasingly being collected electronically [5], much of the information is in free text rather than in a structured form [6], and is difficult to use clinically or for research. Although free text is the most faithful way to represent some types of information, such as patient stories, structured recording of diagnoses and other key items of clinical information is recommended by national guidance from the Professional Record Standards Body (PRSB) [7]. Widespread use of controlled clinical terminologies such as SNOMED CT enables clinical concepts to be recorded in a consistent way, but only if clinicians are able to use the system easily. It can be onerous and time-consuming for clinicians to enter detailed structured information in many EHR systems [6], and time spent on data entry can affect the human experience of clinical consultations [8]. There is a need for methods to facilitate data entry without impeding the clinical workflow.

Overall, free text is common in EHRs and structured fields are under-used, making it difficult to retrieve information for clinical care, research or service planning.

One way to reduce the burden on clinicians entering structured data is to minimise the amount of data that needs to be entered, by improving interoperability and the use of shared health records. There are international standards for the design of health records (openEHR) [9] and standards for communication between systems (Fast Healthcare Interoperable Resources, FHIR) [10]. The PRSB publishes professional requirements for health records and interoperability, which are being converted into technical standards for implementation by 'INTEROPen', a collaboration of UK EHR software companies, NHS Digital and other stakeholders [11].

Structured clinical records could be linked directly to audit and registry reporting systems, avoiding the wasteful double entry that currently takes place. They would also enable rapid research using clinical records for emerging diseases such as COVID-19, avoiding the need for wasteful post-hoc duplication of data entry.

The need for NLP at the point of care

Despite major research initiatives to analyse clinical text, NLP technology has been under-utilised in clinical applications [12]. A fundamental problem is that information extracted from text may be accurate enough for population-level inferences (where a small error rate can be accommodated statistically), but may not be safe for making clinical decisions for individual patients without a Feasibility study of 'MiADE' point of care natural language processing, EDGE number 157134, IRAS number 322887, 13/46 Protocol, Version 1.1, DATE 24/07/2023

clinician in the loop. Even seemingly simple text classification tasks such as negation detection can be prone to error [13]. It is for this reason that it is not possible to use NLP retrospectively to safely populate structured data fields in clinical records. Instead, our proposed NLP solution will analyse free text as soon as it is created, and suggest structured entries which will be verified by the clinician before being committed to the record. These structured data can be used immediately for clinical decision support as well as for secondary uses such as to assist clinical coding, or for research. Immediate user feedback in our design will also enable the system to improve and learn more quickly.

The NHS Common User Interface guidelines [14] contained recommendations for user interfaces incorporating real-time NLP to assist terminology binding. MiADE is an open source system designed around these principles.

Benefits to patients

- Transfers of care a clear, structured summary of diagnoses and treatments is invaluable as a handover to a new team looking after a patient, whether between shifts in hospital, or when patients are discharged or transferred between care settings.
- Decision support and patient safety many EHR systems include automatic warnings of medication allergies and interactions, and automated reminders for monitoring of chronic diseases. All these decision support aids rely on accurate, structured data to be present in the EHR. Clinical error is a major source of patient harm.
- Electronic health records are used in a large number of research studies for patient benefit. All these studies rely on high quality data; missing data can introduce bias and might result in inaccurate study outcomes which can lead to patient harm. If clinically-recorded data are not sufficiently complete, time-consuming retrospective data entry may be needed.
- Clinical trials are vital for developing and evaluating new treatments, but many trials fail to recruit an adequate number of participants [26]. Automated algorithms can help to detect patients eligible for certain trials, but only if the EHR contains high quality data [27].

We believe that all patient groups will benefit, but sicker patients or those with more complex clinical histories may benefit more, as they may be at more risk of harm from clinical error due to missing information.

The proposed NLP system will enable the advantages of structured data to be realised while avoiding the disadvantage of the burden on clinicians entering the data. The patient experience of consultations may also improve if clinicians have to spend less time entering data into the computer [8].

Benefits to the NHS and the wider population

This project will make it easier to use data for purposes beyond individual care. Although existing NLP approaches are being applied to health record databases, data need to be validated before they are used for decisions that may impact patients. Our approach enables immediate validation, and the data can be used for operational research, service planning, audit, safety monitoring and clinical coding in near real time. A recent audit in UCLH estimated that only 62% of diagnoses were included in problem lists.

3. OBJECTIVES AND OUTCOME MEASURES/ENDPOINTS

The overall aim of this study is to evaluate the effectiveness of the MiADE point of care natural language processing (NLP) system for improving the recording of diagnoses, medications and allergies in electronic health records (EHR), and to investigate factors affecting the effectiveness of the system.

3.1 Primary Objective

To ascertain whether the MiADE point of care natural language processing system increases the number of diagnoses, medication and allergies recorded by clinicians in a structured way in the electronic health record.

3.2 Secondary Objective(s)

- To evaluate the usability of the MiADE system
- To evaluate the accuracy and technical performance of the MiADE system
- To evaluate the effect of using MiADE on patient consultations
- To explore how the MiADE system can be improved

3.3 Outcome measures/endpoints

Primary outcome measures:

Study 1 (outpatient): Number of structured entries for diagnoses, medication and allergies recorded by the clinician in outpatient consultations.

Study 2 (inpatient): The proportion of ICD-10 coded billing diagnoses for which a similar SNOMED CT concept is present in the problem list for inpatients, evaluated at the point of discharge.

Secondary outcome measures:

- The proportion of structured data items suggested by MiADE that are accepted by the clinician for entry into the structured record.
- Computing time required per consultation note.
- Clinician and patient perceptions of the MiADE system.
- Changes to consultation workflow or process as a result of using the MiADE systems

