- Regarding the recording of problems or diagnoses:
 - How frequently do you enter problem list entries or diagnoses when seeing a patient in clinic? [Never Rarely Sometimes Usually Always]
 - How easy or difficult did you find it to use the Epic interface for entering problems or diagnoses? [Very difficult – Difficult – Neither easy nor difficult – Easy – Very easy]
 - How important do you feel it is to have structured information about problems in the health record? [Very unimportant – Unimportant – Neither important nor unimportant – Important – Very Important]
- Regarding the recording of medications:
 - How frequently do you enter medications in the structured medications section when seeing a patient in clinic? [Never – Rarely – Sometimes – Usually – Always]
 - How easy or difficult do you find it to use the Epic interface for entering medications in the structured medications section? [Very difficult – Difficult – Neither easy nor difficult – Easy – Very easy]
 - How important do you feel it is to have structured information about medications in the health record? [Very unimportant – Unimportant – Neither important nor unimportant – Important – Very Important]
- Regarding the recording of allergies or medication intolerances:
 - How frequently do you enter allergies or medication intolerances seeing a patient in clinic? [Never – Rarely – Sometimes – Usually – Always]
 - How easy or difficult did you find it to use the Epic interface for entering allergies and medication intolerances? [Very difficult – Difficult – Neither easy nor difficult – Easy – Very easy]

 How important do you feel it is to have structured information about allergies in the health record? [Very unimportant – Unimportant – Neither important nor unimportant – Important – Very Important]

Pre-MiADE questionnaire – inpatient study

- Regarding the recording of problems or diagnoses:
 - How frequently do you enter problem list entries or diagnoses when clerking a patient or reviewing a patient on a ward round? [Never – Rarely – Sometimes – Usually – Always]
 - How frequently do you enter problem list entries or diagnoses when completing a discharge summary? [Never – Rarely – Sometimes – Usually – Always]
 - How easy or difficult did you find it to use the Epic interface for entering problems or diagnoses? [Very difficult – Difficult – Neither easy nor difficult – Easy – Very easy]

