Inpatient clinical teams will be recruited to the study. Within each team, the clinicians (consultants, specialty and foundation doctors who see inpatients) will be recruited, consented and trained. Doctors rotate through clinical teams every few months, so the MiADE system will be switched on for the relevant clinicians at a time point half-way through the four-month rotation, to allow comparison of the completeness of structured recording of diagnoses on the problem list before and after the switch-on. The 'gold standard' of recording of diagnoses will be the ICD-10 coded billing diagnoses which are assigned by the clinical coding team based on a review of the entire medical record after a patient is discharged. Diagnoses will be aggregated by groups of ICD-10 codes similar to a previous UCLH audit [15], and a diagnosis will be considered as included in the problem list if any SNOMED CT concept which maps to an ICD-10 code in the group was recorded on or prior to the patient's discharge date. This flexibility of mapping will be permitted as different professionals may assign different clinical codes to the same condition based on their interpretation and judgement, especially for cases where an exact code does not exist. The proportion of ICD-10 code groups with a problem list entry will be calculated per patient, and aggregated across the patients under the care of the clinical team during the study period.

For a sample of 5 clinicians, semi-structured interviews will be held with the clinicians after they have been using MiADE for at least two weeks, using the same questions as for outpatient doctors except the question on medications, as MiADE for inpatients does not handle medications.

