5.1 Inclusion criteria

Study 1 clinician inclusion criteria: Any interested clinicians who have their own clinic list at UCLH and see outpatients, who consent to be part of the study. A subset of at least 5 clinicians will be purposively sampled to include a range of specialties for the observation substudy, and they will undergo observed consultations.

Study 1 patient inclusion criteria: All outpatients seen by the clinician from 2 months before being consented until 2 months after the MiADE system is switched on for included clinicians. For clinicians selected for observation (at least 5), we will observe at least 2 consultations from one or more clinics before and 2 consultations from one or more clinics after the MiADE system is switched on will be observed. Hence the minimum number of observed consultations will be 20.

Feasibility study of 'MiADE' point of care natural language processing, EDGE number 157134, IRAS number 322887, Protocol, Version 1.1, DATE 24/07/2023

Study 2 clinician inclusion criteria: All clinicians within interested inpatient teams at UCLH.

Study 2 patient inclusion criteria: All inpatients managed under the care of a participating team during the study period.

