10.1 Primary outcome

Study 1 (outpatient): The primary outcome is the difference in the mean number of structured problem list, medication or allergy entries, comparing the time periods with and without MiADE switched on.

Study 2 (inpatient): The primary outcome is the difference in the proportion of ICD-10 discharge diagnoses with a corresponding structured problem list entry, comparing the time periods with and without MiADE switched on.

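### Study 2: inpatient stays in progress at switch-on have mixed MiADE exposure, and keeping them in the primary comparison shrinks the MiADE contrast

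*Protocol*

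**What the plan says.** Five statements in the protocol bear on this.

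- **Reading time.** Section 3.3 scores an ICD-10 diagnosis by whether a similar SNOMED CT concept "is present in the problem list for inpatients, evaluated at the point of discharge". Section 4 (Study 2) counts a concept if it "was recorded on or prior to the patient's discharge date", with no lower limit at switch-on.
- **Switch-on.** Section 4: "the MiADE system will be switched on for the relevant clinicians at a time point half-way through the four-month rotation".
- **Population.** Section 5.1: "All inpatients managed under the care of a participating team during the study period".
- **Contrast.** Section 10.1 takes the difference in proportions "comparing the time periods with and without MiADE switched on". Section 4 has the per-patient proportion "aggregated across the patients under the care of the clinical team during the study period".
- **Volume.** The study summary counts patients by discharge: "assuming 5 inpatient teams each discharge 5 patients per week, and 24 weeks of data are analysed".

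No section says which period a stay belongs to if it begins before switch-on and ends after it. None excludes such stays. The only lag after switch-on (at least two weeks) applies to surveys, observations and interviews.

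**The concern.** Wards already hold patients on the day MiADE is switched on. Those patients were admitted, and partly documented, without it. The inpatient questionnaire in section 4 asks how often problems are entered "when clerking a patient or reviewing a patient on a ward round", so the protocol itself expects recording before the discharge summary. A single reading at discharge cannot separate entries made before switch-on from those made after it.

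If such stays count as post-MiADE, that group includes stays recorded partly without MiADE. If they count as pre-MiADE, that group includes MiADE-assisted entries. Either way the two groups differ less in exposure than the comparison intends. At stake is the size of the estimated MiADE effect, which a feasibility study carries forward to later decisions.

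**Working it through.** **1. The plan's own figure.** Section 10.3 plans for 62% against 70% and states 549 problems per group. It gives no alpha or power; two-sided 5% and 80% are assumed here.

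n = [1.960 × √(2 × 0.66 × 0.34) + 0.842 × √(0.62 × 0.38 + 0.70 × 0.30)]² / 0.08² = (1.313 + 0.562)² / 0.0064 ≈ 549

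At 8.8 problems per patient, 549 / 8.8 = 62.4, the stated 62 patients. The planned difference is reproduced and is the reference below.

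**2. Window and volume.** The end of trial is 8 weeks after the last switch-on (section 7.7), so W = 56 days. Five teams × 5 discharges × 8 weeks = 200 post-MiADE discharges, or 200 × 8.8 = 1,760 problems.

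**3. Share of crossing stays.** With steady flow, the share of discharges in a window of W days that were admitted before it opened is E[min(L, W)] / W. For exponential stays with mean m this is m(1 − e^(−W/m)) / W. The documents give no length of stay, so m = 3, 7 and 14 days are assumptions.

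**4. Effect on the difference.** Points lost = 8 × share × fraction of the effect lost in crossing stays. The maximum takes that fraction as 1.

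| Mean stay (days) | Share, 8 weeks | Most points lost | Points lost if half the effect is lost | Discharges left of 200 |
|---|---|---|---|---|
| 3 | 5.4% | 0.4 | 0.2 | 189 |
| 7 | 12.5% | 1.0 | 0.5 | 175 |
| 14 | 24.5% | 2.0 | 1.0 | 151 |

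**5. Power.** At 549 problems per group, full loss takes power from 80% to about 75%, 69% and 55% (the last taking the share as 14/56 = 25%). In that worst case 80% power needs 991 problems per group, still below the 1,760 expected over 8 weeks. These figures ignore clustering, as section 10.3 does. The main consequence is therefore an estimate that is too small, rather than a lack of problems to analyse.

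**6. The pre-MiADE side.** Section 4 allows as little as 4 weeks between study entry and switch-on. With W = 28 the same formula gives 10.7%, 24.5% and 43.2% of pre-MiADE discharges begun before that window. Those stays are partly untrained. If training raises recording, they lower the pre-MiADE proportion and widen the difference. The size cannot be calculated, because the documents give no training effect.

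**The case against.** The strongest reply is that the protocol never assigns crossing stays to the post-MiADE group, and that allocating boundary stays is normal content for a statistical analysis plan. The first half is right. Discharge-date assignment is only implied, by an outcome read at discharge and volume counted by discharge. But the dilution does not depend on it, since admission-date assignment shrinks the contrast too. The second half stands only in part: section 5.1 fixes an all-inpatients population, so an analysis plan that dropped crossing stays would depart from the protocol.

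Four stronger readings are tempting, and the documents do not support them.

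- *The error can run only towards no effect.* The primary comparison starts after consent and training, and sections 4 and 10.6.4 allow that joining the study may itself change recording. The pre-MiADE overlap in step 6 can act the other way.
- *Crossing stays lose most of the effect.* The questionnaire puts clerking and ward rounds in one item and the discharge summary in another, without ranking them. Later notes can be processed by MiADE, and any entry up to discharge counts. The loss per stay may be small.
- *Longer stays weigh more because they carry more diagnoses.* Section 4 calculates a proportion per patient before aggregating. If those proportions are averaged, they do not.
- *The loss reaches about 3.5 points.* That takes 8 × 43%: a 14-day mean stay, total loss of effect, and the 4-week period that section 10.3 uses to illustrate sample size. It is not the post-MiADE period.

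**Conclusion.** The point holds in limited form. The stated population, reading time and period contrast together leave stays that cross switch-on with mixed exposure, and retaining them shrinks the MiADE contrast under either assignment. Over an 8-week post-MiADE period the loss is at most about 0.4, 1.0 or 2.0 of the planned 8 points for mean stays of 3, 7 or 14 days.

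This rests on assumed exponential stays, steady flow and no catch-up in the crossing stays; catch-up makes the loss smaller. The net direction of all boundary effects is not settled, because stays begun before training may offset part of it. The sample size arithmetic in section 10.3 is not at fault. The matter deserves a change because the remedy is cheap, but with short stays the effect is modest.

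**What to change.** In sections 4 and 10.6.2:

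- Base the primary Study 2 comparison on stays whose admission and discharge both fall within the same period.
- Use pre- and post-MiADE windows of equal length, 8 weeks where available, so that long stays are cut off alike in both. This also deals with stays begun before training.
- Report crossing stays separately, and the result for all discharges as a sensitivity analysis.
- Add admission date to the data extract. Section 9.1 limits the extract to the minimum required, so this should be settled before extraction.

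**Cost.** Over 8 weeks about 5-25% of stays leave the main comparison. The roughly 150-189 that remain of 200 are well above the 62 patients in section 10.3. If windows are only 4 weeks, 11-43% leave; at a 14-day mean stay about 57 of 100 remain, below 62. Long stays are under-represented, equally in both windows, so the main result describes a somewhat shorter-stay population than all inpatients. The sensitivity analysis shows how far that matters.
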